#### Statistical Analysis Addendum

Prior to data analysis the following are revisions were made to the analysis plan.

Multiplicity. The original proposal used alpha=.05 for 3 outcomes in the primary aim. We will use this threshold for all primary and secondary outcomes and provide a post hoc description of familywise error (e.g., families: sleep, CGM, psychosocial outcomes) using Holm's procedure.

Missing data approach. We will conduct our models for aims 1-3 (focal models) using an inclusive strategy incorporating extraneous auxiliary variables to support a conditionally missing at random assumption. We will examine missing data for all variables in our focal models. For variables with substantial missingness (5% or more) we will create a group indicator for missingness (yes, no) and examine effect sizes for extraneous baseline variables, considering those with effect sizes of  $>|.20|$  as being related to missingness. We will also consider extraneous baseline variables with partial correlations  $>|.30|$  with the variables with substantial missing. We will prioritize variables meeting both criteria, then those meeting only the partial correlation criteria. Variables only related to missingness will not improve the model and will not be considered further. Auxiliary variables will be included as additional outcomes in a way that does not affect interpretation of focal variables. If missing not at random is suspected, we will conduct pattern mixture or selection model approaches as sensitivity analyses. All models will be tested using BLIMP 3 software using Markov chain Monte Carlo estimation; we will report Bayesian median point estimates and 95% credible intervals for treatment effect estimates for previously stated models (i.e., MMRM) for aims 1 and 2 and mediation (indirect) effects from path models for aim 3 (see below).

Intention to treat and per protocol. Modeling for aims are based on the intention to treat principle retaining all individuals in their randomly assigned treatment arm. We will conduct per protocol models if more than 5% of participants did not adhere to the protocol, defined as completing at least 80% of sessions. In these models, we will assess for correlates of engagement and include them as control variables in models excluding the participants who did not complete the protocol.

Models for aims 1 and 2 will provide valuable insight into the potential moderators and timing of change in participants. Aim 3 modeling is revised to use a path analysis approach to test separate parallel multiple mediator models for glycemic outcomes (e.g., A1C, time in range). The indirect effects will be tested with Bayesian 95% credible intervals. Correlates of sleep improvement will be used in these models as control variables and explored as moderators of the mediated effect.

**C.2.11 Subject Retention Strategy.** We anticipate a 17% attrition rate. We expect to randomize up to 170 subjects to obtain complete data on 120 subjects. This estimate is based on our previous work. All efforts will be made to retain participants and reduce burden of participation. Assessment visits and coaching calls will be flexibly scheduled according to participant needs. Parking and/or transportation costs will be reimbursed. Participants will be allowed to mail back actigraph and CGM devices to reduce office visits. Participants will receive \$100 for participation, incrementally paid across visits. Participants will also be allowed to keep the Fitbit device as an additional incentive for program completion. Those in the attention control group will receive a Fitbit at the end of the study. Parking will be provided for anyone who chooses to complete their data collection visits in-person.

**C.2.12 Treatment Fidelity Strategy** All coaching sessions (Sleep-Opt and Healthy Living attention control) will be recorded for training and fidelity monitoring (audio or videorecording). All coaches will be trained until they reach a criterion of adherence to the treatment protocol before being assigned study participants. Each quarter, [name] will review approximately 10% of conducted sessions quarterly and code them for adherence using previously developed rating scales. Items include aspects of the session content (e.g., eliciting questions or problems about the intervention, setting goals), structure of the session (e.g., sets an agenda), and therapeutic process (e.g., uses open-ended questions, appropriate session pacing). Control sessions will be reviewed for the presence of sleep-related content or health advice. If any sleep or health advice (other than direction to the source website) is provided, this will trigger re-training. Drs. [name] and

[name] will provide bi-weekly supervision to the coaches for their respective groups, providing back data regarding treatment fidelity as well as troubleshooting any clinical issues. A manual of operations will be developed, and staff will be trained on study procedures. All interactions with participants will be scripted when possible. Protocol violations will be reviewed by the staff and reported to the IRB. All interactions by staff with participants will be logged, and emails will be archived.

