## Sleep Optimization to Improve Glycemic Control in Adults with Type 1 Diabetes

### Abstract

Despite improvements in treatment regimens and technology, less than 20% of adults with type 1 diabetes (T1D) achieve glycemic targets. Sleep is increasingly recognized as a potentially modifiable target for improving glycemic control. Diabetes distress, poor self-management behaviors, and reduced quality of life (QoL) have also been linked to sleep variability and insufficient sleep duration. The American Diabetes Association Standards of Medical Care in Diabetes incorporated sleep as an important component of the medical evaluation in persons with diabetes. However, no specific recommendation was given as to how to improve sleep. A significant gap of knowledge exists regarding the effects of sleep optimization on glycemic control in T1D. The purpose of this study is to determine the efficacy of a T1D-specific sleep optimization intervention (Sleep-Opt) on the primary outcomes of sleep variability, sleep duration and glycemic control (A1C); other glycemic parameters (glycemic variability, time in range), diabetes distress, self-management behavior, QoL, and other patient reported outcomes in working-age adults with T1D and habitual increased sleep variability or short sleep duration. To achieve these aims, we propose a randomized controlled trial in 120 working age adults (18 to 65 years) with T1D. Participants will be screened for habitual sleep variability ( $> 1$  hour/week) or insufficient sleep duration ( $< 6.5$  hours per night). Eligible subjects will be randomized to the Sleep-Opt group or healthy living attention control group for twelve weeks. A one-week run-in period is planned, with baseline measures of sleep by actigraphy (sleep variability and duration), glycemia (A1C and related glycemic measures: glycemic variability and time in range using continuous glucose monitoring), and other secondary outcomes: diabetes distress, self-management behaviors, quality of life and additional patient-reported outcomes. Sleep-Opt is a technology-assisted behavioral sleep intervention that we recently developed that leverages the rapidly increasing public interest in sleep tracking by consumers (+500% in 3 years). Our behavioral intervention employs four elements: a wearable sleep tracker, didactic content, an interactive smartphone application, and brief telephone counseling. The attention control group will participate in a healthy living information program. At midpoint (Week 6) completion (Week 12) and post-program (Week 24), baseline measures will be repeated to determine differences between the two groups and sustainability of the intervention.

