*The goal of this study is to examine whether the Sleep-Opt intervention, a novel intervention to reduce sleep variability and insufficient sleep duration, improves objective sleep and glucose parameters, diabetes distress, self-management behavior, QoL, and other patient-reported outcomes.* Responding to PA-18-330, *Investigator Initiated Clinical Trials Targeting Diseases with the Mission of NIDDK*, we will randomize 120 individuals with T1D and habitual increased sleep variability or insufficient sleep duration to a 12-week **Sleep-Opt** intervention or healthy living control group equal in time and attention. Our novel sleep optimization is based on behavior change principles (self-monitoring, goal setting, motivational enhancement) and employs a wearable sleep tracker, didactic content, and brief telephone counseling tailored to T1D.

**Specific aims:** In 120 working-age adults (18-65 years) with T1D:

**Aim 1:** Determine the effect of the **Sleep-Opt** intervention, compared to an attention control group, on sleep variability, sleep duration and glycemic control (primary outcomes). Rationale: Sleep variability and insufficient sleep duration in T1D adults was associated with higher A1C, possibly related to circadian misalignment and reduced insulin sensitivity. Hypothesis: **Sleep-Opt** will result in improved sleep and glycemic control. Approach Assess sleep variability, sleep duration, and glycemic control as measured by actigraphy and A1C at Week 0 (baseline), Week 6 (mid-treatment), Week 12 (end of treatment) and post treatment Week 24, of **Sleep-Opt** compared to a 12-week healthy living attention control. Secondary outcomes include glycemic variability, time in range and other objectively measured sleep parameters.

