**C.2.3 Participants.** We plan to enroll up to 300 subjects. We anticipate a 40% screen failure rate and expect to randomize up to 170 for a final sample of 120 subjects with complete data. Inclusion criteria: working-age adults, 18-65 years with a clinical diagnosis of T1D for at least one year who reported habitual sleep variability (1 hour/week or more) or sleep duration < 6.5 h/night during work- or weekdays (confirmed with actigraphy) with a desire to improve sleep and who own a smartphone compatible with Fitbit. Exclusion criteria: Insomnia symptoms defined as severe as assessed by the Insomnia Severity Index (score  $\geq 15$ ), being at high risk for obstructive sleep apnea as assessed by and Stop Questionnaire, history of severe hypoglycemia (defined as hypoglycemic episodes that result in loss of consciousness within the last 6 months, seizures, or requiring emergency room visits or hospitalization), A1C  $> 10\%$ , rotating shift or night shift work, use of sleep medications/aids, significant renal impairment (estimated glomerular filtration rate  $< 45$  ml/min/1.73 m^2), significant medical morbidities (such as congestive heart failure, cirrhosis, chronic obstructive pulmonary disease requiring oxygen, active treatment for cancer, restless leg syndrome, depression (PHQ8 score greater than or equal to 10), history of stroke with neurological deficits), or breast feeding, pregnant, or planning pregnancy.

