**C.2.5 Sample size estimation.** We conservatively estimated the minimal detectable difference between treatment arms to be 0.4 to 0.6 standard deviations for our target sample size of 60 per group (after attrition) at the 12-week post-treatment measurement based on a 2-groups pre-post design,  $\alpha = 0.02$ , 2-sided, and 80% power. This represents a modest but clinically important change. Table 4 shows projected estimates for attention controls, based on our pilot data with this population, and the treatment group, based on the minimum detectable difference we could detect as statistically significant given our design, target sample size, and correlations between time points of 0.5 to 0.8. Standard deviations from pilot data for A1C (1.07%), sleep

variability (30 minutes), and sleep duration (49 minutes), and the correlation between measurements ( $r = 0.56$  to 0.85) were used for sample size determination.

Table 4. Minimum detectable treatment effects		
	Control	Treatment
A1C (%)	7.8	7.4
Sleep variability (minutes)	75	57
Sleep duration (minutes)	355	380

Analyses adjusting for the pre-treatment glucose level and other key covariates (e.g., BMI) will increase power. Aim 2 assesses the main effects of secondary outcomes and, similar to the primary aim, will allow us to detect effect sizes of 0.3 to 0.5 or greater as statistically significant. **Adjustment for multiple testing.** Our primary aim uses an adjusted alpha level for multiple primary outcomes. For secondary aims, exploratory, and hypothesis generating analyses we will publish unadjusted p-values and apply

the Benjamini-Hochberg approach to control the family-wise error rate. Aim 3 pertains to correlations between change measures of sleep and glucose control parameters, for which we will be able to detect correlations of the magnitude of .25 or greater as statistically significant.

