mg/dL), percentage of time < 70 mg/dL, and percentage of time spent  $\geq 180$  mg/dL. Interstitial glucose measurements with FreeStyle Libre and Dexcom were found to be accurate compared with capillary blood glucose reference values with a mean absolute relative difference (MARD) of 12% and 9% respectively compared to the gold standard YSI measure of blood glucose. Accuracy of 10% MARD have been approved for self-adjustment of insulin doses in clinical practice. Glycemic measures will be obtained for one week at baseline and Weeks 6, 12, and 24. In our pilot study we experienced a 10% sensor failure rate (less than 15% failure rate reported by the manufacturer and may be due to the team's expertise in placing these devices). Most sensor failure was due to dislodgement. If dislodgement occurs, we will overnight mail a new sensor to the study participant. The dislodged sensor retains the recorded data. Participants will be instructed to return the sensor. We anticipate a 24-hour disruption in data collection with dislodgement.

**C.2.9b Wrist actigraphy to measure behavioral sleep** Participants will wear an Actiwatch Spectrum Plus (Respironics, USA) on their non-dominant wrist for one week during baseline assessment, and Weeks 6, 12 and 24. Data will be collected in 30-sec epochs. Actiwatch records activity, light exposure, and wear time. Subjects will be asked to keep a daily sleep log and press an event marker on the Actiwatch at bedtime and wake-up time. Data will be downloaded and reviewed with each participant to clarify inconsistencies when the Actiwatch is returned. Rest intervals will be set using reported try-to-fall-asleep times and wake-up times on daily sleep logs or event markers if these times are missing. Using the Immobile Minutes algorithm in the Actiware 6 software, we will derive the following variables: sleep onset, sleep offset, sleep duration, sleep efficiency (a measure of sleep quality), mid-sleep time (time point between sleep onset and wake time), and standard deviation (SD) of sleep duration, an indicator of sleep variability which we previously showed to be related to glucose metabolism.

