### 3.1 Protection of Human Subjects

#### 1. Risks to Human Subjects

##### a. Human Subjects Involvement, Characteristics, and Design

**Study Design.** The purpose of this study is to determine the efficacy of a T1D-specific sleep optimization intervention (Sleep-Opt) on the primary outcomes of glycemic control (A1C), sleep variability and sleep duration; and secondary outcomes: other glycemic parameters (glycemic variability, time in range); diabetes distress, self-management behavior, quality of life (QoL) and other patient reported outcomes in working-age adults with T1D and habitual high sleep variability or short sleep duration. The human subjects involved in this research will be working-age adults, 18-65 years with type 1 diabetes (T1D) who report habitual sleep variability (sleep duration SD > 1 hour per week) or sleep duration <6.5h/night during the work days with a desire to improve sleep. To achieve these aims, we will conduct a randomized controlled trial comparing a sleep intervention to a healthy living attention control group.

**Study population.** We plan to enroll up to 300 subjects. We anticipate a 40% screen failure rate and expect to randomize up to 170 for a final sample of 120 subjects with complete data. Inclusion criteria include 18-65 years of age, with a clinical diagnosis of T1D for at least one year, report habitual sleep variability (1 hour/week or more) or sleep duration <6.5h/night during the work days or week days (confirmed with actigraphy), with a desire to sleep longer, and who own a smartphone compatible with Fitbit. Exclusion criteria include insomnia symptoms defined as severe insomnia symptoms as assessed by the Insomnia Severity Index (score  $\geq 15$ ), being at high risk for obstructive sleep apnea as assessed by Stop Questionnaire, a history of severe hypoglycemia (defined as hypoglycemic episodes that result in loss of consciousness within the last 6 months, seizures, or requiring help from others), A1C  $> 10\%$ , rotating shift or night shift work, use of sleep medications/aids, significant renal impairment (estimated glomerular filtration rate  $< 45 \text{ ml/min/1.73 m}^2$ ), significant medical morbidities such as congestive heart failure, cirrhosis, chronic obstructive pulmonary disease requiring oxygen, active treatment for cancer, depression (PHQ8  $\geq 10$ ), history of stroke with neurological deficits, breastfeeding, pregnant or planning pregnancy.

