### **3.3 Data Safety Monitoring Plan**

This study will involve working adults (aged 18 to 65 years) with type 1 diabetes (T1D) who experience high sleep variability or insufficient sleep duration. We plan to enroll up to 300 subjects for a final sample size of 120. Subjects will be enrolled and will complete a 1-week run-in period to collect baseline data, actigraphy to measure sleep, and continuous glucose monitoring (CGM) to calculate baseline glycemic variability. Following the run-in period, eligible subjects will be assigned to one of two groups: attention control group = 12 weeks or intervention group = 12 weeks.

The risk associated with this study is minimal for the interventions and data collection methods employed in the study. The potential for a serious adverse event is very low. Drs. [name], [name], and [name] are experts in the clinical care of people with diabetes. [name] has extensive experience with advanced statistics. [name] will assure that participants are fully informed and consent freely, and Drs. [name] and [name] will monitor the safety of the study as described below.

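### The planned number randomised, attrition rate and completer target do not agree: 17% attrition and 120 completers imply about 145 randomised, while the text gives up to 170 or 120 and Table 11's entries sum to 140, not 144

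*Combined protocol and SAP*

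**What the plan says.** Three places give a randomised number together with a completer number. C.2.11 (Subject Retention Strategy) reads "We anticipate a 17% attrition rate. We expect to randomize up to 170 subjects to obtain complete data on 120 subjects". C.2.3 (Participants) reads "We anticipate a 40% screen failure rate and expect to randomize up to 170 for a final sample of 120 subjects with complete data". Section 3.1 (Study population) repeats "expect to randomize up to 170 for a final sample of 120 subjects with complete data". The 17% appears only in C.2.11, and it is the only attrition rate in the document.

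C.2.5 (Sample size estimation) bases the detectable effect on "our target sample size of 60 per group (after attrition", so there 120 is what remains after losses. Section 3.3 agrees in calling 120 the final sample: "We plan to enroll up to 300 subjects for a final sample size of 120".

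The Specific Aims differ: "we will randomize 120 individuals with T1D and habitual increased sleep variability or insufficient sleep duration". The Abstract describes a randomised trial in 120 adults without saying whether that is the number entering or the number completing.

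Table 11 (C.2.13) lists entrants per arm by month over 37 enrolment months, a row of active subjects, and a running total that ends at 144 in Year 4 month 7.

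**The concern.** An attrition rate, a completer target and a randomised number are tied together: any two fix the third. Here the plan states all three side by side and they do not fit, a fourth figure (120 randomised) appears in the Specific Aims, and the accrual table reaches none of the randomised numbers in the text. A reader cannot tell whether planned retention is 83% (17% attrition) or 71% (120 of 170), or what losses the margin above 145 is meant to absorb. If the Specific Aims wording were followed literally, the trial would finish with fewer participants than its own sample-size statement assumes.

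**Working it through.** **Inputs.** Attrition 17% (C.2.11). Completer target 120, that is 60 per group after attrition (C.2.5). Randomised: up to 170 (C.2.3, C.2.11, 3.1) or 120 (Specific Aims). Two-sided alpha .02, 80% power, a two-group pre-post design and correlations of 0.5 to 0.8 (C.2.5). Monthly entrants from Table 11.

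**1. The plan's own detectable effect.** I take the two-sample noncentral-t detectable difference and multiply it by √(2(1 − r)) for a change score. At 60 per group it is 0.585 SD at r = 0.5 and 0.370 SD at r = 0.8. This reproduces the stated 0.4 to 0.6 SD.

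**2. Number to randomise.** Completers/(1 − attrition) = 120/0.83 = 144.6, so 145. The looser form 120 × 1.17 gives 141. Neither is 170.

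**3. What 170 implies.** 170 × 0.83 = 141.1 completers. Going from 170 to 120 is a loss of 50/170 = 29.4%. If the 17% is dropout only, a further 1 − 120/141.1 = 15.0% of those retained would have to have incomplete data. The margin over 145 is 170 − 145 = 25.

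**4. What 120 randomised implies.** 120 × 0.83 = 99.6, or 49.8 per group. On the basis of step 1 with r = 0.5, the detectable effect is 0.644 SD, just outside 0.6. With baseline adjustment (factor √(1 − r²) in place of √(2(1 − r))) it is 0.558 SD, inside the range.

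**5. Table 11 totals (both arms together).**

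| Year | Entrants | Sum |
|---|---|---|
| 1 | 6 × 4 | 24 |
| 2 | 10 × 4 + 2 × 2 | 44 |
| 3 | 10 × 4 + 2 × 2 | 44 |
| 4 | 7 × 4 | 28 |
| Total | | 140 |

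The printed total is 144. The break is in Year 2 months 8 and 9: each shows one entrant per arm, two in all, but the running total goes 52, 56, 60 where the entries give 52, 54, 56. Year 3 has the same entries and adds them correctly (100, 102, 104). At 17%, 140 leaves 116.2 completers and 144 leaves 119.5.

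**6. Table 11 active counts.** Assume six months on study per entrant, inferred from the Year 1 rise (4 to 24) and the Year 4 run-off (20 to 4). The printed entries then give 22, 20, 20, 20, 20 for Year 2 months 8 to 12. The table prints 22, 22, 24, 24, 24.

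**7. Sensitivity of power.** On the basis of step 1, for r from 0.8 to 0.5:

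| Randomised | Completers per group | Detectable effect (SD) |
|---|---|---|
| 170 | 70.5 | 0.34 to 0.54 |
| 140 | 58.1 | 0.38 to 0.595 |
| 120 | 49.8 | 0.41 to 0.64 |

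**The case against.** **170 is a ceiling.** Every mention says up to 170, and randomising about 145 would respect it and yield 120. This stands: a reader might infer that 170 is an error or that the plan cannot reach its target, and neither follows. What remains is an unexplained margin set beside a rate that does not produce it. A reader might also object that 300 enrolled with 40% screen failure leaves 180, not 170. Both figures are upper limits, so that is not a contradiction.

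**Complete data may be stricter than not dropping out.** The analysis section expects some missing data, and the addendum sets a rule for variables with 5% or more missing. The idea is therefore present, but no rate is given. Sensor failure does not supply the further 15%, because dislodged sensors are replaced and keep their recorded data: "We anticipate a 24-hour disruption in data collection with dislodgement". C.2.5 also describes the 60 per group as what is left after attrition.

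**Only the Specific Aims clearly treat 120 as the number randomised.** This is correct. C.2.3, C.2.5, C.2.11, 3.1 and 3.3 all treat 120 as the final or completing number, so the conflict is one sentence against the rest.

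**Power is hardly touched.** This largely stands. A reader might infer an underpowered trial from the 0.64 SD. That figure needs 120 randomised, alpha .02, an unadjusted change score and r near 0.5 together; it is 0.60 at r = 0.56, the lowest pilot correlation. The planned model adjusts for baseline, which gives 0.56 even at r = 0.5. The analysis is also intention to treat and uses all available data, so completers are a planning figure.

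**Monitoring.** A reader might infer that the monitoring committee will judge the trial against a wrong attrition figure. Section 3.3 lists cumulative randomisation, retention and attrition as report contents but sets no benchmark for them.

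**Conclusion.** The figures are inconsistent as written, with modest consequence. The stated 17% and 120 completers lead to about 145 randomised. The 170 is compatible only as a maximum with an unexplained margin of about 25, or as an expected number with an unstated total loss of about 29%. Randomising 120 conflicts with 60 per group after attrition, since about 50 per group would remain.

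Table 11 is wrong by four in its total. Year 3's correct addition of the same entries makes the Year 2 running total the likelier slip. This is not certain, because 144 is also the figure that fits 17% and 120 (24/144 = 16.7%). The active-count mismatch rests on the inferred six-month stay; the gap between 140 and 144 does not.

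The detectable effect moves little across 140 to 170 randomised, and no conclusion about an underpowered trial is warranted.

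**What to change.** State one expected randomised number, one loss rate and one completer target, and use them in the Specific Aims, C.2.3, C.2.11, section 3.1 and Table 11.

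- On the plan's own figures: about 145 randomised (146 for equal arms), 17% attrition, 120 completers. Label 170 as a maximum and say what the margin covers.
- If 170 is the expected number, state a total loss of about 29% and how it splits between dropout and incomplete data. Table 11 would then need about 170/37 = 4.6 entrants per month, against 140/37 = 3.8 now, or more enrolment months.
- Reword the Specific Aims so that 120 is the number with complete data, and make the Abstract match.
- Correct Table 11 so that entries, active counts and running totals agree with each other and with the chosen number.

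The cost is wording and one table. The design and analysis do not change.
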